6.4.4 Hand-foot-skin reaction: will dose reduce both sorafenib and 5-FU CI

Recommended dose modification for hand foot skin reaction							
Toxicity Grad	le	Suggested dose modification					
Grade 1	Any occurrence	Maintain dose level and consider topical therapy for symptomatic relief					
Grade 2 1 st occurrence		Maintain dose level and consider topical therapy for symptomatic relief If no improvement within 7 days, see below					
	No improvement within 7 days or 2 nd occurrence	Hold Sorafenib until resolved to Grade 0-1 When resuming treatment, decrease dose by one dose level ¹					
	3 rd occurrence	Hold Sorafenib until resolved to Grade 0-1 When resuming treatment, decrease dose by two dose levels ²					
	4 th occurrence	Discontinue Sorafenib permanently					
Grade 3	1 st occurrence	Hold Sorafenib and 5-FU until resolved to Grade 0-1 When resuming treatment, decrease Sorafenib dose by one dose level ¹ and decrease 5-FU by 25%					
	2 nd occurrence	Hold Sorafenib and 5-FU until resolved to Grade 0-1 When resuming treatment, decrease Sorafenib dose by one dose level ¹ and decrease 5-FU by 50%					
	3 rd occurrence	Discontinue treatment permanently					

¹ If the patient is at the second dose reduction level (Sorafenib 200mg po QD) already, Sorafenib will be discontinued,

²If the patient is at the first dose reduction level (Sorafenib 400mg po QD) or the second dose reduction level (Sorafenib 200mg po QD) already, Sorafenib will be discontinued,

At first occurrence of HFSR, independent of grade, prompt institution of supportive measures such as topical emollients, low potency steroids, or urea-containing creams should be administered.

Recommended prevention/management strategies for skin toxicities consistent with HFSR are summarized below.

Recommended Prevention/Manager Foot-Skin-Reaction	nent Strategies for Skin Toxicities Consistent with Hand-
Toxicity Grade	Practical Prevention / Management Strategies for HFSR
Grade 0 (Preventive strategies)	Maintain frequent contact with trial physician to ensure early diagnosis of HFSR. Practical prevention strategies Pedicure ^a for subjects with pre-existing hyperkeratosis. Subjects should avoid hot water, and clothing or activities

	that can cause friction on the skin.				
	Moisturizing cream should be applied sparingly.				
	Padded gloves and open shoes with padded soles should be				
	worn to relieve pressure points.				
	Continue preventive strategies and in addition:				
Grado 1	Soak hands in cool water.				
	Apply petroleum jelly to moist skin.				
Any occurrence	In the case of hyperkeratotic lesions, exfoliate the hands or				
	feet and apply moisturizing cream immediately afterwards.				
Grade 2 Any occurrence or	Continue supportive/management measures and add				
Grade 3 Any occurrence	analgesic(s) for pain.				
a: Pedicure should be done by a podiatrist.					

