6.4.1 Dose Reduction Levels

The starting dose of sorafenib is 400 mg twice a day. Study medication will be administered daily on a continuous basis.

Doses will be delayed or reduced for clinically significant hematologic and nonhematologic toxicities that are related to protocol therapy according to the guidelines shown in the Dose Delays/Dose Modifications table that follows. Dose modifications will follow predefined dose levels: Dose adjustments for hematologic toxicity are based on the blood counts obtained in preparation for the day of treatment.

Dose modification levels for sorafenib							
Dose	Sorafenib						
Starting Dose	400 mg twice daily						
1 st Dose Reduction Level	400 mg once daily						
2 nd Dose Reduction Level	200 mg once daily						

Recommended Dose Modification of sorafenib for Hematologic Toxicities										
Toxicity	ANC(x 10 ⁹ /L)	Hemoglobin (g/dL)	Platelets (x 10 ⁹ /L)	Sorafenib						
Grade 1	<lln-1.5< td="">< LLN – 10.0	<lln-75< td="">Treat on time No change	</lln-75<>	</lln-1.5<>	< LLN – 10.0	<lln-75< td="">Treat on time No change	</lln-75<>	Treat on time No change						
Grade 2	≥ 1.0 to < 1.5	< 10.0 - 8.0	≥ 50 to < 75	Treat on time No change						
Grade 3	≥ 0.5 to < 1.0	< 8.0 - 6.5	≥ 25 to < 50	Treat on time Reduce by one dose level						
Grade 4	< 0.5	Life-threatening consequence; urgent intervention indicated	<25	Delay sorafenib until toxicity resolves to Grade 2 or less then Reduce by two dose levels ¹						
Febrile Neutropenia				Sorafenib held until toxicity has resolved to Grade 2 or less; when sorafenib is restarted, reduce by one dose level ²						

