Doses of sorafenib that have been reduced for any reason will not be re-escalated. For treatment-related non-hematologic toxicities, patients who do not recover to Grade 1 toxicity within 3 weeks will go off Sorafenib for the duration of the study, but they can continue with FOLFOX if they continue to meet treatment criteria for FOLFOX.

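### Hand-foot skin reaction table: the third Grade 2 row can never lead to resuming sorafenib, so at 400 mg once daily a milder reaction can end sorafenib where a worse one does not

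*Combined protocol and SAP*

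**What the plan says.** Section 6.4.1 gives three sorafenib doses: 400 mg twice daily at the start, 400 mg once daily as the first reduction, and "200 mg once daily" as the second. There is no level below that. The text closing section 6.4.5 adds: "Doses of sorafenib that have been reduced for any reason will not be re-escalated".

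The table in section 6.4.4 is laid out by grade, with numbered occurrences inside each grade.

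- **Grade 2, first occurrence:** the dose is kept.
- **Grade 2, row beginning "No improvement within 7 days or 2" (that is, or a second occurrence):** sorafenib is held, then resumed one level lower under footnote 1.
- **Grade 2, third occurrence:** sorafenib is held, then "When resuming treatment, decrease dose by two dose levels", under footnote 2.
- **Grade 2, fourth occurrence:** "Discontinue Sorafenib permanently".
- **Grade 3, first occurrence:** sorafenib and 5-FU are held; sorafenib resumes one level lower under footnote 1, "and decrease 5-FU by 25" per cent.
- **Grade 3, second occurrence:** one further sorafenib level, and a 50% cut in 5-FU.
- **Grade 3, third occurrence:** treatment stops permanently.

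Footnote 1 reads "If the patient is at the second dose reduction level (Sorafenib 200mg po QD) already, Sorafenib will be discontinued". Footnote 2 applies the same stop to a patient at either reduced dose, 400 mg or 200 mg once daily.

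**The concern.** The third Grade 2 row describes a return to treatment, and the next row sets a separate rule for a fourth occurrence. Both presuppose that some patients are back on sorafenib after a third Grade 2 reaction, yet the footnote and the bar on re-escalation appear to leave none.

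If so, the less severe reaction can take sorafenib away in a position where the more severe one would not. Elsewhere in section 6.4, the only single cut of two levels ("Reduce by two dose levels", in the hematologic table of section 6.4.1) is reserved for Grade 4; Grade 3 there costs one level.

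This table is likely to be used. Section 2.4 reports hand-foot skin reaction in 73% of patients on sorafenib with capecitabine and oxaliplatin, and Grade 3 hand-foot syndrome in 20% on sorafenib with FOLFOX. Under section 6.0 a patient who loses sorafenib may stay on study on FOLFOX alone. What is at stake is therefore who remains on the combination under test, and how the tolerability results read.

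**Working it through.** No sample-size or power figure is involved. The check follows every path through the table.

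**Inputs.** Daily doses are 800 mg (400 mg twice daily), 400 mg, 200 mg and 0 (stopped), from section 6.4.1. The rules are the section 6.4.4 rows with footnotes 1 and 2, and the bar on re-escalation is from section 6.4.5. Occurrences are counted within grade, as the rows are nested.

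**Step 1: dose at a third Grade 2 occurrence.** The second occurrence has removed one level, so the dose is at most 400 mg once daily and cannot rise. The third occurrence therefore happens at 400 mg or 200 mg once daily. Footnote 2 stops sorafenib at both, so it resumes at 0 of the 2 possible doses. No patient is on sorafenib with three Grade 2 reactions behind them, so the fourth row is never reached.

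**Step 2: all on-drug states reachable from 400 mg twice daily.** Entries are sorafenib in mg/day after the next reaction. The bracketed figure applies if a first Grade 2 reaction does not improve within 7 days.

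| Current dose | Prior Grade 2 | Prior Grade 3 | After next Grade 2 | After next Grade 3 |
|---|---|---|---|---|
| 800 | 0 | 0 | 800 (400) | 400 |
| 800 | 1 | 0 | 400 | 400 |
| 400 | 1 | 0 | 200 | 200 |
| **400** | **2** | **0** | **0** | **200** |
| 400 | 0 | 1 | 400 (200) | 200 |
| 400 | 1 | 1 | 200 | 200 |
| 200 | 2 | 0 | 0 | 0 |
| 200 | 1 | 1 | 0 | 0 |
| 200 | 2 | 1 | 0 | 0 |
| 200 | 0 | 2 | 200 (0) | 0 |
| 200 | 1 | 2 | 0 | 0 |

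Of 11 states, exactly one gives less sorafenib after a Grade 2 than after a Grade 3 reaction. The difference is 200 − 0 = 200 mg/day, and 200/800 = 25% of the starting dose. On the Grade 3 branch, 5-FU from full dose (section 5.1.2) becomes 2400 × 0.75 = 1800 mg/m².

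**Step 3: earlier cuts for other toxicities.** Allowing patients to arrive at 400 mg or 200 mg once daily for other reasons adds four states, 15 in all. The same single state is at fault.

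**Step 4: the table with a one-level third row and footnote 1.** The bold state now goes to 200 mg once daily after a third Grade 2 reaction. That adds one state (200 mg, three Grade 2, no Grade 3), making 12, or 16 with reduced arrival doses. None is inverted. From the new state a fourth Grade 2 reaction reaches the fourth row and stops sorafenib. A third occurrence now resumes at 1 of the 2 possible doses.

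**The case against.** **The counting rule is not stated.** If occurrences ran across grades, a Grade 3 reaction after two Grade 2 reactions would be a third occurrence and would stop treatment, so the inversion would vanish. This stands as a condition on the inversion. The layout favors counting within grade, and no text says otherwise. It does not rescue the third Grade 2 row: a second occurrence of either grade costs one level, so a third would still fall at a dose where footnote 2 stops sorafenib, and the fourth row would still be dead.

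**The rule may be a deliberate, conservative choice.** The Grade 3 branch also reduces 5-FU, and section 6.1 lists palmar-plantar erythrodysesthesia in 42-82% of patients on continuous infusion. A retry of sorafenib after cutting a second likely cause is defensible. So is stopping after repeated Grade 2 reactions despite a sorafenib reduction. But that reasoning does not explain a written instruction to resume that can never be used, nor a separate stop one occurrence later.

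**The investigator always has a clear action, and the path is narrow.** Both are true. Footnote 2 resolves each case to a stop. To reach the inverted state, the first Grade 2 reaction must improve within 7 days and there must be no other sorafenib reduction. The table is also headed as recommended or suggested. These points limit the reach of the fault without removing it.

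**The fourth row would still add little after the change.** Every fourth Grade 2 reaction would occur at 200 mg once daily, where a one-level cut already means stopping. That is correct; the row would then be consistent with the rest of the table, though not decisive.

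**Conclusion.** The concern holds. The impossible resumption and the unreachable fourth row follow from the table, its footnotes and the bar on re-escalation, however occurrences are counted. The reversal of severity holds when they are counted within grade. It is confined to sorafenib and to one state of 11: 400 mg once daily, two Grade 2 reactions, no Grade 3. There the sorafenib outcome is 0 against 200 mg/day. At 200 mg once daily a third Grade 2 reaction and a Grade 3 reaction both stop sorafenib.

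States are not patients. The documents give no basis for estimating how many of the 40 will reach this one. The effect is on exposure to the combination and on the tolerability findings, with no change to sample size, power or the definition of TTP.

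**What to change.** Amend the third-occurrence Grade 2 row of section 6.4.4 to a one-level reduction on resuming, marked with footnote 1. A patient at 400 mg once daily then resumes at 200 mg once daily, and a patient at 200 mg once daily stops. Keep the permanent stop at the fourth occurrence. Footnote 2 can then be removed from this table, since no other row there uses it. One added sentence saying that occurrences are counted within grade would settle the other ambiguity.

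Simply rewriting the third row as a stop would tidy the table but leave the reversal of severity in place.

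The cost is a one-row amendment with no extra visits or tests. The downside is somewhat longer exposure at 200 mg once daily for a few patients with recurrent Grade 2 reactions. The table already accepts that dose for the same patient after a Grade 3 reaction, although with 5-FU reduced as well.

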6.4.5 Treatment-emergent hypertension

Hypertension is a known and potentially serious AE associated with sorafenib treatment. Subjects will undergo brief physical examinations, including blood pressure monitoring, on a weekly basis through the first 5 weeks of therapy. Thereafter, blood pressure will be monitored on Day 1 and 15 of each cycle.

Blood pressure measurements that are out of the normal range must be reported by the treating physician. Blood pressure measurements considered out of the normal range are diastolic pressure > 90 mm Hg and/or systolic pressure > 140 mm Hg, or a 20 mm Hg increase in diastolic pressure if the previous measurement was within normal limits. The dose-modification schedule to be followed in the event of treatment-emergent hypertension is outlined below. The choice of anti-hypertensive medication to be used in cases of treatment-emergent hypertension will be at the investigator's discretion and based on site-specific treatment guidelines as applicable. All anti-hypertensive medications used for the management of treatment-emergent hypertension should be recorded in the patient's records.

Management of Treatment-Emergent Hypertension							
Grade of Event (NCI-CTCAE v4.0)	Management/ Next Dose						
Grade 1	Consider increasing blood pressure monitoring. Continue sorafenib dosing as scheduled.						
Grade 2 asymptomatic and diastolic pressure 90-99 mm Hg	Begin anti-hypertensive therapy. Continue sorafenib dosing as scheduled.						
Grade 2 (symptomatic/persistent)	Sorafenib should be held ^a until symptoms resolve and						
OR	diastolic blood pressure < 90 mm Hg; also treat subject						
Grade 2 symptomatic increase by >	> with anti-hypertensives and when sorafenib is restarted,						
20 mm Hg (diastolic) or to systolic BP	BP reduce by 1 dose level. ^b						

Management of Treatment-Emergent Hypertension								
> 140 mm Hg or diastolic BP>90 mm HG if If diastolic blood pressure is not controlled (< 90 mm Hg								
previously within normal limits	on anti-hypertensive therapy, reduce another dose							
OR	level. ^b							
Grade 3								
Grade 4	Discontinue sorafenib							
a: Subjects requiring a delay of > 21 days should discontinue sorafenib unless, in the opinion of the								

treating physician, the subject may benefit from continued treatment.

b: Subjects requiring dose reductions beyond 200 mg every day, should discontinue sorafenib.

Doses of sorafenib that have been reduced for any reason will not be re-escalated. For treatment-related non-hematologic toxicities, patients who do not recover to Grade 1 toxicity within 3 weeks will go off Sorafenib for the duration of the study, but they can continue with FOLFOX if they continue to meet treatment criteria for FOLFOX.

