3.2 Exclusion Criteria

- The patient has either clinically apparent central nervous system metastases or carcinomatous meningitis
- The patient is a woman who is pregnant or lactating. Women of childbearing potential must have a negative serum pregnancy test performed within 7 days prior to the start of study drug. Post-menopausal women (defined as no menses for at least 1 year) and surgically sterilized women are not required to undergo a pregnancy test. All patients (men and women) of childbearing potential must agree to use adequate contraception beginning at the signing of the ICF until at least 30 days after the last dose of study drug. The definition of adequate contraception will be based on the judgment of the principal investigator or a designated associate.
- Active or clinically significant cardiac disease including:
 - Congestive heart failure New York Heart Association (NYHA) > Class II.
 - Active coronary artery disease.
 - Cardiac arrhythmias requiring anti-arrhythmic therapy other than beta blockers or digoxin.
 - QTc > 500 ms
 - Unstable angina (anginal symptoms at rest), new-onset angina within 3 months before randomization, or myocardial infarction within 6 months before randomization.
- Evidence or history of bleeding diathesis or coagulopathy.
- Subject with any pulmonary hemorrhage/bleeding event of NCI-CTCAE v4.0 Grade 2 or higher within 4 weeks before enrollment; any other hemorrhage/bleeding event of NCI-CTCAE v4.0 Grade 3 or higher within 4 weeks before enrollment.
- Presence of a non-healing wound, non-healing ulcer, or bone fracture.
- History of organ allograft. (including corneal transplant).
- Any malabsorption condition.

- Uncontrolled hypertension defined as systolic blood pressure > 150 mmHg or diastolic pressure > 90 mmHg, despite optimal medical management.
- Uncontrolled ascites defined as not easily controlled by stable doses of diuretics.
- Known human immunodeficiency virus (HIV) infection.
- The patient has a medical or psychiatric condition that constitutes an unacceptable risk for participation in this trial, in the judgment of the treating physician.
- The patient has received any investigational agents within 4 weeks prior to their first dose of sorafenib.
- ECOG status of ≥ 2
- Child-Pugh B or C cirrhosis (CTP score \geq 7) (See Appendix A)
- CLIP score >3 (See Appendix A) Inability to comply with study and/or follow-up procedures

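### Section 6.4.5 can hold sorafenib for systolic hypertension, but its only pressure test for restart and for the further reduction is diastolic

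*Combined protocol and SAP*

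**What the plan says.** Section 6.4.5 gives both pressure components equal standing when it says which readings must be reported: "Blood pressure measurements considered out of the normal range are diastolic pressure > 90 mm Hg and/or systolic pressure > 140 mm Hg". A diastolic rise of 20 mm Hg from a normal value also counts.

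The table in that section then sets the dose-modification schedule. Its hold row is entered by symptomatic or persistent Grade 2, by Grade 3, or by a symptomatic Grade 2 increase. The wording for that last trigger includes "20 mm Hg (diastolic) or to systolic BP" and continues in the next fragment of the split cell with above 140 mm Hg, or diastolic above 90 mm Hg, if previously normal.

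Once sorafenib is held, the row requires that symptoms resolve and adds one pressure condition, "diastolic blood pressure < 90 mm Hg; also treat subject". Sorafenib restarts one dose level lower. A further reduction follows under the sentence beginning "If diastolic blood pressure is not controlled (< 90 mm Hg", which applies to patients on anti-hypertensive treatment.

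The row that starts treatment without a hold is labelled "Grade 2 asymptomatic and diastolic pressure 90-99 mm Hg".

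Two time limits sit nearby. Footnote a to the table says a delay beyond 21 days should end sorafenib, unless the treating physician sees possible benefit in continuing. The closing text of 6.4.5, on treatment-related non-hematologic toxicity, says "patients who do not recover to Grade 1 toxicity within 3 weeks will go off Sorafenib" for the rest of the study, and gives no such exception.

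**The concern.** The hold can be triggered by one pressure component and released on the other. A patient whose abnormality is systolic may go back on drug with that abnormality unchanged, and the sentence meant to catch poor control after restart does not look at it.

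The protocol itself describes hypertension on sorafenib as potentially serious, and presents the table as the schedule to follow. Two investigators could handle the same patient differently, one restarting on the literal wording and the other waiting for systolic pressure to fall, and neither would have departed from the text. What is at stake is patient safety and consistent dosing. Nothing in Section 14 depends on it.

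**Working it through.** The plan states no figure on this point, so the check is a side-by-side reading. The table was broken in extraction, but both columns can be recovered and the reading does not depend on where the break falls.

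**1. Which component each rule uses (all in 6.4.5)**

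| Rule | Systolic | Diastolic |
|---|---|---|
| Out-of-range definition | > 140 | > 90, or a 20 mm Hg rise from normal |
| Hold: symptomatic Grade 2 increase | to > 140 | rise > 20, or to > 90 |
| Hold: symptomatic/persistent Grade 2; Grade 3 | by grade, not limited to a component | by grade, not limited to a component |
| Restart (with symptoms resolved) | none | < 90 |
| Further reduction | none | not controlled (< 90) |
| Asymptomatic Grade 2: treat and continue | none | 90-99 |

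**2. One patient through the row.** Take an illustrative reading of 155/80 mm Hg in a symptomatic patient who was previously normal.

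- Out of range? Yes: 155 > 140.
- Hold? Yes, through the row's own wording for a symptomatic Grade 2 increase. No outside grading cut-off is needed.
- Restart pressure condition met when the hold begins? Yes: 80 < 90. Only the symptom condition remains.
- When symptoms resolve with pressure still at 155/80: restart one level lower is permitted.
- Still out of range? Yes: 155 > 140.
- Further-reduction sentence triggered? No: 80 < 90.

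**3. The asymptomatic row.** A Grade 2 rise that is systolic only, without symptoms and not persistent, does not match the 90-99 diastolic label. It does not match the hold row either. No row clearly covers it.

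**4. Does another section supply a systolic release condition?** None does.

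- 6.4.3 leaves hypertension out of its table.
- 7.5.5 allows anti-hypertensives at the investigator's discretion and refers back to Section 6.0 for dose changes.
- 6.5 lists general reasons for stopping treatment.
- 3.2 does use systolic pressure ("Uncontrolled hypertension defined as systolic blood pressure > 150 mmHg or diastolic pressure > 90 mmHg" despite optimal management), but as an entry criterion.
- The closing text of 6.4.5 says when sorafenib stops for good, not when it may restart.

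**5. Is the time limit itself consistent?** Three weeks is 21 days, so footnote a and the closing text meet at the same point. For a patient held longer than 21 days who has not recovered to Grade 1, footnote a lets the physician continue and the closing text does not. The opening of Section 6.0 also caps sorafenib interruption at 3 weeks, whatever the reason.

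**6. Comparison within Section 6.** Other sorafenib holds are released on the grade scale that triggered them: hand-foot skin reaction at Grade 0-1 (6.4.4), Grade 4 hematologic toxicity at Grade 2 or less (6.4.1), and other Grade 3 non-hematologic toxicity at Grade 2 or less (6.4.3). The hypertension row is released on one pressure component instead.

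**The case against.** The strongest reply is that the row does much more than test diastolic pressure. It requires anti-hypertensive treatment. It lowers the dose by one level, and the closing text of 6.4.5 makes that reduction permanent. For the one trigger that names systolic pressure, symptoms must be present, so their resolution is a real condition. Persistent Grade 2 or Grade 3 systolic elevation after restart brings the patient back into the row for another hold and reduction, and footnote b ends sorafenib once reductions would go below 200 mg daily. Sections 6.5 and 7.5.5 leave room for judgment, and the release wording permits restart without compelling it. The out-of-range definition governs reporting and the 3.2 criterion governs entry, so neither is a restart rule.

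All of that stands, and it rules out stronger readings. A reader might infer that the hold has no effect for isolated systolic hypertension, or that continuing systolic elevation can never lead to a second reduction. The documents do not support either: the row's other requirements still apply, and re-entry is a second route to reduction. A reader might also infer that an asymptomatic patient at, say, 175/85 could restart on the day of the hold. That depends on how CTCAE v4.0 grades the reading, and the documents do not print those cut-offs.

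What the reply does not remove is the mismatch within the row. None of these safeguards makes systolic pressure a condition of restart or of the further-reduction sentence.

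**Conclusion.** The point holds as an internal inconsistency in 6.4.5. Systolic pressure can start a hold, but it is not a condition for ending one or for the further-reduction sentence. The asymptomatic Grade 2 row leaves a related gap, and footnote a conflicts with the closing text on what happens after 3 weeks. The worked case assumes only a symptomatic, previously normal patient at 155/80.

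The number of patients affected cannot be derived. Section 6.4 lists hypertension at 17% for sorafenib, which for 40 patients is 0.17 × 40 = 6.8, about 7. It gives no grade and no pressure component. A reader might apply an assumed isolated-systolic share of 20-50% and get 6.8 × 0.2 = 1.4 to 6.8 × 0.5 = 3.4 patients. That would treat every hypertensive patient as held, although Grade 1 and the asymptomatic Grade 2 row continue dosing, so it is not a usable estimate.

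The point bears on safety and consistent dosing, not on the TTP hypothesis or the sample size. It is worth correcting because the written rule itself gives the inconsistent result.

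**What to change.** The sponsor and investigator should reconcile four parts of 6.4.5 with each other and with the section's out-of-range definition: the hold triggers, the restart condition, the further-reduction condition and the asymptomatic Grade 2 row. They should also reconcile these with footnote a and with the Grade 1 recovery rule in the closing text. Which thresholds and clinical rules result is for them to decide; none is proposed here.

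The cost is a wording amendment. Blood pressure is already checked weekly through the first 5 weeks and then on Days 1 and 15 of each cycle, so no assessments are added.

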6.0 DOSE MODIFICATION / TOXICITY MANAGEMENT

Study drug treatment will be modified in the event of certain adverse events, as shown in the tables below.

- Regardless of the reason for holding study drug treatment, the maximum allowable length of treatment interruption of FOLFOX is 6 weeks (the holding of 3 consecutive doses) and of Sorafenib is 3 weeks. If the patient needs to stop FOLFOX due to toxicity, they can stay on study as long as they continue with Sorafenib. If the patient needs to stop Sorafenib due to toxicity, they can stay on the study as long as they continue FOLFOX. If they need to stop both FOLFOX and Sorafenib for longer than the above time limits, they must be taken off the study and the Principle Investigator must be notified.
- Doses of chemotherapy that have been reduced will not be re-escalated.
- No held doses of Sorafenib or FOLFOX will be made up. If a patient misses a dose for toxicity, the patient will proceed to the next treatment day or cycle as scheduled.

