6.4.3 Dose modification for non-hematologic toxicities¹

Recommended dose modification for non-hematologic toxicity (excluding hypertension and hand foot skin reaction, diarrhea and fatigue.									
Grade	Dose Interruption	Dose Modification							
• Grade 0-2	Treat on time	No Change							
• Grade 3	Interrupt until ≤Grade 2	DECREASE one dose level							
• Grade 4	OFF protocol therapy	OFF protocol therapy							
 If no recovery after 21 day delay, treatment will be discontinued unless subject is deriving clinical benefit 									

¹For sorafenib dose reductions for diarrhea, nausea, and vomiting, see sections 6.3.4.1 and 6.3.4.2.

For HFSR, sorafenib and 5-FU should be both reduced; For diarrhea, sorafenib, 5-FU and oxaliplatin should all be reduced; For fatigue, sorafenib, 5-FU and oxaliplatin should all be reduced.

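### After Grade 3 non-hematologic toxicity, Section 6.4.3 restarts sorafenib at Grade 2, but the closing rule of Section 6.4.5 stops it for good unless Grade 1 is reached within 3 weeks

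*Combined protocol and SAP*

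**What the plan says.** Four places in the protocol govern when sorafenib is held, restarted or stopped for non-hematologic toxicity.

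- **Section 6.4.3, table.** Its title limits it: "Recommended dose modification for non-hematologic toxicity (excluding hypertension and hand foot skin reaction, diarrhea and fatigue". Within that scope, Grade 0 to 2 means dosing on schedule without change. Grade 3 means "Interrupt until ≤Grade 2", followed by a reduction of one dose level. Grade 4 ends protocol therapy. The last row adds: "If no recovery after 21 day delay, treatment will be discontinued unless subject is deriving clinical benefit".
- **Section 6.4.5, closing paragraph.** It stands after the hypertension table but opens "For treatment-related non-hematologic toxicities" and continues that "patients who do not recover to Grade 1 toxicity within 3 weeks will go off Sorafenib for the duration of the study". FOLFOX may go on if its own criteria are met. The paragraph contains no exception.
- **Section 6.4.5, hypertension table, footnote a.** A delay of more than 21 days leads to discontinuation unless, in the view of the "treating physician, the subject may benefit from continued treatment".
- **Section 6.0, first bullet.** Whatever the reason for the hold, "the maximum allowable length of treatment interruption of FOLFOX is 6 weeks (the holding of 3 consecutive doses) and of Sorafenib is 3 weeks". It names no recovery grade.

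Neither 6.4.3 nor the closing paragraph of 6.4.5 refers to the other, and nothing says which prevails.

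**The concern.** The two rules use different grades to mean recovered: Grade 2 in Section 6.4.3 and Grade 1 at the end of Section 6.4.5. The time limits are equal, so the difference lies in the grade and in the exception, not in the number of days.

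The consequence is the permanent loss of one component of the regimen. Section 5.1 describes a single-arm trial and Section 14.1 plans 40 patients, so there is no concurrent control in which the same ambiguity would also operate. Under one reading a patient continues on reduced sorafenib with FOLFOX. Under the other, the same patient receives FOLFOX alone from then on. The patient's progression time counts toward the primary endpoint either way, but the treatment behind it differs. Tolerability is a secondary objective (Section 1.2), and the same course would be recorded as a dose reduction under one rule and a sorafenib discontinuation under the other. Section 5.2.4 restricts the correlative studies to patients treated at one hospital, which implies that others are treated elsewhere. Different readings at different clinics are therefore possible.

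**Working it through.** The plan states no figure on this point, so there is nothing to reproduce. The check sets the rules side by side and runs cases through them.

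**Inputs**

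- Restart grade in 6.4.3: Grade 2 or less.
- Recovery grade in the closing paragraph of 6.4.5: Grade 1.
- Time limits: 21 days in 6.4.3 and 3 weeks in the closing paragraph. 3 × 7 = 21, so they are equal in length.
- Exception after the limit: clinical benefit in 6.4.3, possible benefit in footnote a of 6.4.5, none in the closing paragraph, none in 6.0.
- Overlap in scope: treatment-related non-hematologic toxicities other than the four named in the 6.4.3 table title. The footnote to that table also sends nausea and vomiting to separate rules.

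**Cases** (the day numbers are illustrative)

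| Case | Section 6.4.3 | Closing paragraph of 6.4.5 | Compatible? |
|---|---|---|---|
| A. Grade 3, falls to Grade 2 on day 10, still Grade 2 on day 21 | Restart on day 10 one level lower, then continue | Off sorafenib permanently at 3 weeks | No |
| B. Grade 2 from onset, never held, lasting more than 3 weeks | Dosing unchanged | Off sorafenib if read literally; not engaged if the rule applies only after a hold | Depends on reading |
| C. Still Grade 3 after a 21-day delay, deriving clinical benefit | Discontinuation not required | Off sorafenib permanently | No |
| D. Grade 3, falls to Grade 1 or less within 3 weeks | Restart one level lower | Rule not triggered | Yes |
| E. Grade 4 | Off protocol therapy | Not needed | No conflict on recovery grade |

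Case A is decisive because it involves a hold and so does not depend on how the word recover is read. One might try to apply the rules in sequence: restart on day 10 under 6.4.3, then stop on day 21 under 6.4.5. That does not reconcile them. From day 21 on, 6.4.3 still directs unchanged dosing for a Grade 2 toxicity, and it nowhere describes the restart as provisional. The closing paragraph also does not say whether its 3 weeks run from onset or from the start of the hold.

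Case C is a separate mismatch, on the exception. Section 6.0 does not resolve A, because it sets no recovery grade. On C it has no exception either, so it also differs from 6.4.3 and from footnote a.

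**Comparison inside the protocol.** For chemotherapy, Section 6.3.3.5 resumes at Grade 1 or less and also ties its 6-week limit to Grade 1, so restart grade and recovery grade agree. The hand-foot skin reaction table in 6.4.4 resumes at Grade 0 to 1, which agrees with the closing paragraph. The mismatch is therefore specific to the 6.4.3 table.

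**Number of patients.** This would need the rate of Grade 3 toxicity within the table's scope and the share that settles at Grade 2. The documents give neither. Section 6.4 lists sorafenib event rates (for example rash/desquamation 40%, increased lipase 41%, hypophosphatemia 40%) without a split by grade. Section 2.3 describes drug-related Grade 3 and 4 events on sorafenib as infrequent, without a figure.

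**The case against.** The best defense is that the closing paragraph concerns only toxicities that led to a hold. Its 3 weeks match the maximum interruption in 6.0 and the 21-day delay in 6.4.3. Section 6.3.3.5 points the same way: it treats Grade 2 at full chemotherapy dose, yet ends with a rule removing patients who have not recovered to Grade 1 within 6 weeks. Read literally, that would remove lasting Grade 2 patients whom the same table treats at full dose. This part stands. A reader might infer that every patient with stable Grade 2 toxicity gets opposite instructions, but the documents do not establish that for toxicity that was never held (case B). The argument does not touch case A.

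A reader might also bring in the hypertension table, where one Grade 2 row says "Begin anti-hypertensive therapy. Continue sorafenib dosing as scheduled". That row covers asymptomatic patients with diastolic pressure of 90 to 99 mm Hg. The next row holds sorafenib for symptomatic or persistent Grade 2, so the table does not tell clinicians simply to continue in lasting Grade 2 hypertension. Fatigue and hand-foot skin reaction add nothing to the grade conflict either, since the 6.4.3 table excludes them.

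It is tempting to size the problem from the persistent neuropathy rates in Section 6.2 (48% all grades, 6% Grade 3 or 4). Those come from a colorectal trial of oxaliplatin with 5-FU/LV, without sorafenib. They give no Grade 2 share. Neurologic toxicity has its own table in 6.3.3.4, which does not mention sorafenib. They also say nothing about Grade 3 toxicity that improves to Grade 2. They support no count here.

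Finally, the primary analysis is not damaged in form. Section 10.2 defines TTP from initial treatment to progression or death, stopping sorafenib is neither an event nor a stated censoring rule, and the patient may stay on study with FOLFOX. Section 4.0 sends issues that would delay treatment to the Principal Investigator, which limits divergence in part. This stands and lowers the severity; it does not remove the contradiction.

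**Conclusion.** The contradiction is real and can be seen from the text alone. For a treatment-related toxicity within the 6.4.3 table, a Grade 3 event that settles at Grade 2 for more than 3 weeks receives incompatible instructions on permanent discontinuation of sorafenib. A second mismatch concerns whether a patient who is benefiting may continue beyond 21 days.

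The conclusion assumes that the closing paragraph of 6.4.5 applies beyond hypertension, as its general wording indicates. It does not depend on the never-held Grade 2 case, which stays open until the scope of the rule is stated.

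The size cannot be given as a patient count. By arithmetic, each affected patient is 1/40 = 2.5% of the planned sample, but how many there would be is unknown. It would go too far to say that the TTP result is undermined: its definition, the hypothesis and the sample size are untouched. What is affected is sorafenib exposure, the tolerability record, and the interpretation of TTP as an effect of the combination. The text is wrong as written, with moderate severity.

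**What to change.** Reconcile Section 6.4.3 and the closing paragraph of Section 6.4.5, together with the interruption limit in Section 6.0 and footnote a of the hypertension table. The same wording in 6.4.3 and the closing paragraph should state:

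1. one recovery grade for sorafenib after non-hematologic toxicity;
2. whether the 3-week rule applies only to toxicities that caused a hold or to all, and from which date the 3 weeks are counted;
3. whether a clinical-benefit exception exists after 21 days.

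The paragraph should also sit under a heading that shows its scope, since it now follows the hypertension table. Which grade and which exception apply is a clinical decision for the investigator; this review takes no position on it.

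The cost is one clarifying amendment with IRB approval under Section 13.1. It needs no new patients, procedures or change to the analysis. If patients have already been managed under the present text, the report should list those whose sorafenib was restarted at Grade 2 or stopped for failure to reach Grade 1, so that exposure and discontinuation rates can be interpreted.
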